## 5.0 Initial Screening Questions - Updated 9/13

(Note: You must answer every question on this page to proceed).

If you are converting to the new form, check questions 5.4, 5.6, 5.7, 5.8 and 5.10 before saving and continuing to the next section.

### 5.1 \* Application type:

- Full Committee
- Expedited
- Exempt

### 5.2 \* Risk level (Help Text updated 9/13):

- Minimal risk
- Greater than minimal risk

### 5.3 \* Subject contact:

- Yes (including phone, email or web contact)
- No (limited to medical records review, biological specimen analysis, and/or data analysis)

### 5.4 \* Funding (past or present):

- Funded or will be funded (external sponsor, gift, program or specific internal or departmental funds)
- Unfunded (no specific funds earmarked for this project)
- Unfunded student project

**5.5 \* The Principal Investigator and/or one or more of the key study personnel has financial interests related to this study:**

- Yes  No

If **Yes**, the Conflict of Interest Advisory Committee (COIAC) office may contact you for additional information.

**5.6 \* This is an investigator-initiated study:**

- Yes  No

**5.7 \* This study ONLY involves retrospective records review and/or identifiable biospecimen analysis:**

- Yes  No

**5.8 \* This is a clinical trial:**

- Yes  No

**Clinical Trial Registration**

"NCT" number for this trial:

NCT02729311

**5.9 \* This is a multicenter study:**

- Yes  No

**5.10 \* This application involves the study of unapproved or approved drugs, devices, biologics or in vitro diagnostics:**

- Yes  No

**5.11 \* This application involves a Humanitarian Use Device:**

- No
- Yes, and it includes a research component
- Yes, and it involves clinical care ONLY

**5.12 \* This study involves human stem cells (including iPS cells and adult stem cells), gametes or embryos:**

- No
- Yes, and requires CHR and GESCR review
- Yes, and requires GESCR review, but NOT CHR review

**5.13 \* This is a CTTR study (e.g. the NCT CTTR will be the ITR of record):**

Yes  No

#### 5.14 \* This application includes a request to rely on another IRB (other than NCI CIRB):

Yes  No

Note: If this request is approved, the CHR will **NOT** review and approve this study. Another institution will be the IRB of record.

## 6.0 Expedited Review Categories

#### 6.1 \* If you think this study qualifies for expedited review, select the regulatory category(ies) that the research falls under:

- Category 1: A very limited number of studies of approved drugs and devices
- Category 2: Blood sampling
- Category 3: Noninvasive specimen collection (e.g. buccal swabs, urine, hair and nail clippings, etc.)
- Category 4: Noninvasive clinical procedures (e.g. physical sensors such as pulse oximeters, MRI, EKG, EEG, ultrasound, moderate exercise testing, etc.)
- Category 5: Research involving materials (data, documents, records, or specimens) that were previously collected for either nonresearch or research purposes
- Category 6: Use of recordings (voice, video, digital or image)
- Category 7: Low risk behavioral research or research employing survey, interview, oral history, focus group, program evaluation, human factors evaluation, or quality assurance methodologies

## 7.0 Funding

#### 7.1 Identify all sponsors and provide the funding details. If funding comes from a Subcontract, please list only the Prime Sponsor: **Note: we require only a P Number OR an A Number for funding coming through UCSF. Please avoid these common errors in funding documentation:**

- **DO NOT add the A Number if a P Number was already provided OR update the A Number field when a new funding cycle begins. The IRB does NOT use this information or want these changes made.**
- **DO NOT add a grant continuation as a new funding source.**

External Sponsor:

View Details	Sponsor Name	Sponsor Type	Awardee Institution:	Contract Type:	Project Number	UCSF RAS System Award Number ("A" + 6 digits)
	Alzheimer's Association, Inc.	07	UCSF	Grant	P0508185	

Sponsor Name: Alzheimer's Association, Inc.

Sponsor Type: 07

Sponsor Role:	
Awardee Institution::	UCSF
Is Institution the Primary Grant Holder:	Yes
Contract Type:	Grant
Project Number:	P0508185
UCSF RAS System Award Number ("A" + 6 digits):	
Grant Number for Studies Not Funded thru UCSF:	
Grant Title:	Paired Integrative Exercise Program for People with Dementia and Caregivers
PI Name: (If PI is not the same as identified on the study.)	
Explain Any Significant Discrepancy:	

Gift, Program, or Internal Funding (check all that apply):

Funded by gift (specify source below)  
 Funded by UCSF or UC-wide program (specify source below)  
 Specific departmental funding (specify source below, if applicable)

List the gift, program, or departmental funding source:

[name]; Tideswell/Pepper Foundation UCSF-RAP grant; UCSF-RAP

**7.2 If you tried to add a sponsor in the question above and it was not in the list, follow these steps:**

- If funding has already been awarded or the contract is being processed by the Office of Sponsored Research (OSR) or Industry Contracts Division (ICD), your sponsor is already in the system and the project has an eProposal Proposal or Award number. Check with your department's OSR Staff or ICD Officer to ask how the sponsor is listed in the UC sponsor list and what the Proposal or Award number is. [Click here to find your OSR staff](#) and [here to find your ICD staff](#).
- If your sponsor is not yet in the list, enter it in the box below.

Sponsor not in list

**Only** if your sponsor is not yet in the list, type the sponsor's name:

UCSF-Osher Center RAP grant

**If the funding is administered by the UCSF Office of Sponsored Research, your study will not receive CHR approval until the sponsor and funding details have been added to your application.**

**7.3 \* This study is currently supported in whole or in part by Federal funding OR has received ANY Federal funding in the past (Help Text updated 9/13):**

Yes  No

If **yes**, indicate which portion of your grant you will be attaching:

The Research Plan, including the Human Subjects Section of your NIH grant or subcontract

- For other federal proposals (contracts or grants), the section of the proposal describing human subjects work
- The section of your progress report if it provides the most current information about your human subjects work
- The grant is not attached. The study is funded by an award that does not describe specific plans for human subjects, such as career development awards (K awards), cooperative agreements, program projects, and training grants (T32 awards) OR UCSF (or the affiliate institution) is not the prime recipient of the award

### 8.3 Check any research programs this study is associated with:

- Cancer Center
- Center for AIDS Prevention Sciences (CAPS)
- Global Health Sciences
- Immune Tolerance Network (ITN)
- Neurosciences Clinical Research Unit (NCRU)
- Osher Center
- Positive Health Program

## 9.0 Studies Involving Other Sites

#### 9.1 UCSF is the coordinating center:

Yes  No

If **Yes**, describe the plan for communicating safety updates, interim results, and other information that may impact risks to the subject or others among sites:

If **Yes**, describe the plan for sharing modification(s) to the protocol or consent document(s) among sites:

#### 9.3 Are the above UC campuses requesting to rely on UCSF's IRB (check all that apply):

- Yes (Submit a reliance request through the UC IRB Reliance Registry)
- No (Complete IRB Approval Certification section)

## 10.0 Outside Site Information

#### 10.1 Outside Site Information

Click "Add a new row" to enter information for a site. Click it again to add a second site again to add a third site, a fourth site, etc.

#### For Federally-funded studies only, corresponding FWA#:

\_\_\_\_\_

#### \* The research at this site will be reviewed by:

- The non-affiliated site's IRB or a private IRB
- The non-affiliated site is requesting UCSF to be the IRB of record for this study
- The non-affiliated site is not engaged in the human subjects research and has provided a letter of support

If the other site's IRB approval letter is available now, attach it to the application. If the IRB approval letter is not yet available, submit it once you receive it.

Or, if the other site is **not engaged** in human subjects research, attach the letter of support to your application.

#### For Federally-funded studies only, corresponding FWA#:

\_\_\_\_\_

#### \* The research at this site will be reviewed by:

- The non-affiliated site's IRB or a private IRB
- The non-affiliated site is requesting UCSF to be the IRB of record for this study
- The non-affiliated site is not engaged in the human subjects research and has provided a letter of support

If the other site's IRB approval letter is available now, attach it to the application. If the IRB approval letter is not yet available, submit it once you receive it.

Or, if the other site is **not engaged** in human subjects research, attach the letter of support to your application.

## 11.0 Study Design

### 11.1 \* Study design (Help Text updated 9/13):

We propose to perform a randomized, controlled trial (RCT) with a delayed start design to examine the effects of the Paired PLIÉ program in individuals with cognitive impairment and their care partners over 9 months. Study participants will be 60 pairs of individuals with mild-to-moderate cognitive impairment and their primary care partners. Study pairs will be enrolled in blocks of 10 and will be randomly assigned to Group 1 (immediate start, n=5) or Group 2 (3-month delayed start, n=5). Pairs randomized to Group 1 will participate together in the Paired PLIÉ program 2 days/week for 12 weeks (24 classes total) while pairs randomized to Group 2 will continue with their usual activities. After 3 months, Group 1 will transition into a maintenance phase, and Group 2 will participate in the Paired PLIÉ program 2 days/week for 12 weeks. Outcome data will be collected in all study participants at baseline and 3, and 6 months. We have partnered with local community-based organizations that have agreed to serve as study sites and to assist with recruitment efforts.

We will conduct a sub-study with semi-structured interviews in a sub-sample of our participants. The goal is to assess motivations and barriers for home practice of the exercises taught in the intervention classes and to develop improved support materials (brochures, video clips on DVD and/or YouTube) according to feedback from participants.

### 11.2 If this is a clinical trial, check the applicable phase(s) (Help Text updated 9/13):

- Phase I
- Phase II
- Phase III
- Phase IV

## 12.0 Scientific Considerations

### 12.1 Hypothesis (Help Text updated 9/13):

This study has a hypothesis:

- Yes
- No

If yes, state the hypothesis or hypotheses:

Hypothesis 1: The immediate start group will experience significantly greater improvements in participant outcomes including cognitive function (Alzheimer's Disease Assessment Scale-cognitive subscale, ADAS-cog), independence (Disability Assessment for Dementia, DAD) and quality of life (Quality of Life in Alzheimer's Disease, QOL-AD) compared to the delayed start control group.

Hypothesis 2: The immediate start group will experience significantly greater reductions in caregiver burden (Caregiver Burden Inventory, CBI) and improvements in positive feelings about caregiving (Positive Aspects of Caregiving, PAC) compared to the delayed start control group.

There are no hypotheses for the sub-study.

#### **12.2 \* List the specific aims:**

Aim 1. To determine whether Paired PLIÉ improves participant outcomes over 9 months.

Aim 2. To determine whether Paired PLIE improves caregiver outcomes over 9 months.

Sub-Study: To develop improved support material for home practice.

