#### **12.3 Statistical analysis:**

All primary analyses will be performed using intent-to-treat principles. Baseline characteristics will be compared using descriptive statistics (e.g., frequency tables and percentages for categorical variables; means, medians, standard deviations, ranges for continuous variables), and p-values will be calculated using appropriate statistical tests (e.g., chi-square, t-test, Mann-Whitney). Our primary analytic approach will be mixed effects linear regression which will enable efficient estimation of intervention effects and inclusion of all subjects in intent-to-treat analyses. Analyses will focus on differences in outcomes between the groups over time. Fixed effects terms will be included for group (immediate vs. delayed start), time (0, 3, 6 or 9 months), and the interaction between group and time, with time modeled as a dummy variable. Subjects and cohorts will be modeled as random effects. Models also will adjust for any baseline differences between groups that may occur by chance. Covariates will be included to adjust for any co-interventions that may occur (e.g., medication changes). Sensitivity analyses will be performed to determine the effects of compliance on intervention effects. Graphs and diagnostic tests will be used to assess for outliers and influence points. Line plots will be used to visually examine change over time by group.

Sub-Study: We will conduct qualitative analyses of the transcribed audio recordings from 10 interviews..

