## **13.0 Background**

### 13.1 Background:

More than 5 million Americans are currently living with Alzheimer's disease and related dementia (ADRD), and prevalence is expected to rise to 14 million by the year 2050. Current dementia medications are associated with relatively small effect sizes and are often discontinued due to side effects. However, there is growing evidence that non-pharmacologic interventions can help reduce symptoms in those who are affected as well as caregivers. The available evidence suggests that multi-domain programs—those that combine physical, mental and social stimulation with caregiver education—are more likely to impact multiple outcomes, yet few multi-domain programs have been rigorously tested and disseminated to the community.

We recently developed a novel, multi-domain, non-pharmacologic program called Paired PLIÉ (pronounced 'plee-ay' and stands for Preventing Loss of Independence through Exercise). The original PLIÉ program was developed and tested at an adult day center with affected individuals and trained exercise instructors, where there was evidence of improvement with PLIÉ versus standard chair-based exercises. Effect sizes were moderate to large in both affected individuals and caregivers (see below). Over the past year, we have adapted PLIÉ to be performed with affected individuals and their primary care partners (Paired PLIÉ), including creation of an illustrated booklet and videos to support home-based practice. **The primary objective of the proposed study is to test the efficacy of the Paired PLIÉ program on participant and caregiver outcomes over 9 months.**

**Sub-Study:** According to feedback from study participants, most dyads have difficulties performing regular exercises at home. The 30-minute video we had supplied did not seem to be effective in supporting home practice. We are now planning a qualitative sub-study to determine whether improving support material in form of brochures or shorter video clips can enhance the motivation and feasibility of home exercises.

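### The aims claim efficacy over 9 months, but Group 2 is an untreated control only to month 3, so the month-6 and month-9 group differences do not measure the programme's effect

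*Combined protocol and SAP*

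**What the plan says.** Section 12.2 gives Aim 2 as "To determine whether Paired PLIE improves caregiver outcomes over 9 months"; Aim 1 is parallel for the affected individuals. Section 13.1 states the primary objective as being to "test the efficacy of the Paired PLIÉ program on participant and caregiver outcomes over 9 months". Hypothesis 1 in 12.1 reads "The immediate start group will experience significantly greater improvements in participant outcomes" than the delayed start control group. Hypothesis 2 makes the parallel claim for caregivers, and neither names a visit.

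Section 11.1 describes the control condition. Group 1 takes 24 classes over 12 weeks "while pairs randomized to Group 2 will continue with their usual activities". Then: "After 3 months, Group 1 will transition into a maintenance phase, and Group 2 will participate in the Paired PLIÉ program", on the same schedule.

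Section 12.3 fits a mixed model with group, time (0, 3, 6 or 9 months, as dummy variables) and their interaction, and says: "Analyses will focus on differences in outcomes between the groups over time". It names no primary visit or contrast. It does not say how months 6 and 9 are to be read once both groups have had the programme.

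The sections disagree on whether month 9 is measured. Section 11.1 lists outcome data at baseline, 3 and 6 months. Section 12.3, the assessments paragraph of 16.1 and the caregiver schedule in 16.6 include month 9.

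**The concern.** The aims, the objective and the hypotheses are worded as if Group 2 stayed a control for 9 months. It is a control for 3. From then on the randomised comparison is between two groups that have both been offered the programme, one of them 3 months later than the other. A group difference at month 6 or 9 therefore reflects how the benefit changes after the classes end, and an effective programme can produce a zero or a negative value there.

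Two things are at stake. If a month-6, month-9 or averaged difference is taken as the programme effect, a programme that works can look null, diluted or reversed. If instead the month-3 result is used to claim 9-month efficacy, the claim goes beyond the period in which an untreated group existed. With no contrast named, the choice between these readings can be made after the results are seen.

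**Working it through.** **Inputs.** Standardised pilot effects 0.83, 0.76 and 0.49 (13.2). Correlation between measures 0.75, alpha 0.05, 30 per group, 1 pre and 3 post measures (14.4). Assumed here: a two-sided normal test, the same correlation at all lags, no cohort effect, and no dropout unless stated. All figures are in SD units.

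**The plan's own figure.** For the mean of three post measures minus baseline, the variance factor is (1 + 2×0.75)/3 + 1 − 2×0.75 = 0.333.
- n per group at 80% power = 2 × (1.960 + 0.842)² × 0.333 / d², which is 21.8, so 22, for d = 0.49, and 7.6, so 8, for d = 0.83.
- At 30 per group and d = 0.49, SE = √(0.333 × 2/30) = 0.149 and power is 90.8%.

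This matches the 8 to 22 per group and the 91% in 14.4. An analysis of covariance gives 7 to 18 per group and a post-only comparison 19 to 55, so neither matches. The power basis thus fits a group difference present on average over all three post visits.

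**What the group differences estimate.** Let e0, e3 and e6 be the programme effect at the end of the classes and 3 and 6 months later, assumed equal in both groups. Relative to no programme, at months 0, 3, 6 and 9:
- Group 1: 0, e0, e3, e6
- Group 2: 0, 0, e0, e3

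The group-by-time coefficients are therefore c3 = e0, c6 = e3 − e0 and c9 = e6 − e3. Their average is (c3 + c6 + c9)/3 = e6/3.

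**Numbers for e0 = 0.49:**

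| Benefit after the classes | c3 | c6 | c9 | Average |
|---|---|---|---|---|
| Lasts fully | 0.49 | 0 | 0 | 0.163 |
| Gone within 3 months | 0.49 | −0.49 | 0 | 0 |
| Halves every 3 months | 0.49 | −0.245 | −0.12 | 0.041 |
| Full at 3 months, gone by 6 | 0.49 | 0 | −0.49 | 0 |

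**Chance of a significant result, 30 per group, change from baseline:**
- Month-9 contrast: 5%, equal to alpha, in each of the first two rows.
- Average of three contrasts: 0.163/0.149 = 1.10, so 19.5% under full persistence and 5% in the second row.
- Joint 3-df interaction test: the covariance of (c3, c6, c9) is (2/30) × 0.25 × (I + J), where I is the identity and J the matrix of ones. The noncentrality is 60 × (sum of squares − (sum)²/4). This is 10.8 under full persistence (power 79.6%) and 28.8 in the second row (99.8%). The test is more likely to be significant when the benefit is lost.
- Month-3 contrast: SE = √(0.5 × 2/30) = 0.183, power 76.5% (81.8% if baseline-adjusted).

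**What the same coefficients can give.** c3 + c6 = e3 and c3 + c6 + c9 = e6. With exchangeable correlation:
- e3: factor 6 − 4.5 = 1.5, SE = √(1.5 × 2/30) = 0.32. Baseline-adjusted: 2×0.4375 + 2×0.1875 = 1.25, SE 0.29.
- e6: factor 12 − 9 = 3.0, SE = √(3.0 × 2/30) = 0.45. Baseline-adjusted: 3×0.4375 + 6×0.1875 = 2.44, SE 0.40.
- The 95% half-width for e6 is 1.96 × 0.40 to 0.45, or 0.8 to 0.9 SD. Power for a fully lasting effect is 20 to 23% at 0.49 and 46 to 54% at 0.83.

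**The case against.** The strongest reply is that the planned model is sound. Dummy-coded time with the interaction fits all three coefficients. Month 3 is a clean randomised comparison with usual activities, and months 3 and 6 together separate lasting benefit (0.49, 0) from early loss (0.49, −0.49). A reader might infer from the zero at month 9 that the stated analysis cannot answer the aims at all. The documents do not support that: the information is in the fitted model, and what is missing is a statement of which contrast answers which question.

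A second reply is that no section says success will be judged at month 6 or month 9. The hypotheses name no visit, and over 9 months may describe the length of the trial, as it does in 11.1. This stands in part. It cannot be said that an effective programme will be reported as a failure, only that the plan leaves that reading open. The wording of the objective as efficacy over 9 months and the three-post-visit power basis both point towards it.

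Third, the expressions for c6 and c9 depend on the programme working equally well whether started at month 0 or month 3. If an earlier start is better, c6 and c9 can be positive, as the hypotheses predict, and the sums proposed below are biased. This stands in full. The expressions also need the period after the classes to be alike in both groups, and 11.1 mentions a maintenance phase for Group 1 only.

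Last, a reader might take month 9 to be zero for any benefit that disappears. It is zero only if the loss is complete within 3 months of the last class; the third and fourth rows of the table are not zero.

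**Conclusion.** The point holds in this form. The unconfounded comparison of programme with no programme covers 3 months, while the aims and the objective claim 9. Under equal benefit at either start time, the month-6 and month-9 group differences are e3 − e0 and e6 − e3. They are zero if the benefit lasts fully and zero or negative if it fades. Month 9 alone cannot tell full persistence from loss within 3 months, and the three-visit average is one third of a fully lasting effect. None of these should be read as programme efficacy.

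This goes beyond missing detail, because the readings that the text invites give null, diluted or reversed results for a programme that works. It falls short of saying that the analysis must fail, since the month-3 effect is valid as planned. The contrast expressions rest on the equal-effect assumption; the SEs and powers also rest on correlation 0.75 at all lags and 30 per group with no dropout.

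**What to change.** 1. In 12.1, 12.2 and 13.1, state efficacy against usual activities as a month-3 question, and describe months 6 and 9 as persistence after the programme.
2. In 12.3, name the month-3 group-by-time contrast (c3) as the efficacy test, and state that the month-6 and month-9 group differences are not read as programme effects.
3. From the same model, report c3 + c6 (3 months after the programme) and, if month-9 data are collected, c3 + c6 + c9 (6 months after), with confidence intervals. Label both as secondary and state the equal-effect assumption beside them.
4. Reconcile 11.1 with 12.3, 16.1 and 16.6 on whether outcomes are collected at month 9.

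The cost is wording and two linear combinations of coefficients already estimated; no patients, and no visits beyond those already listed in 16.1, are added. The price is a more modest 9-month claim, because the persistence intervals are wide. The 91% in 14.4 also does not carry over to month 3: for 0.49 SD, power there is 77 to 82% with 30 per group and 67 to 73% with 24 per group after 20% attrition. For 0.76 and 0.83 SD it stays above 95%.
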